D.1. Design and Randomization: Subjects will be drawn from Fetter Health Care Network (FHCN). It is the sole FQHC center in the 4-county area (8 clinics) and provides ~60% of routine AA healthcare in the 4 county area.¹⁰⁷ A support letter from the FQHC network is included. EMR files indicated they have ~2,619 AAs (21-59 yrs old; mean age=45.3yrs) with sole diagnosis of uncontrolled HTN. We will use the 8 practice sites in a 2 arm RCT design (n=192) with clinic as unit of randomization and patient as unit of analysis. All primary healthcare providers across the 8 clinics have agreed to participate if selected. Each clinic has a minimum of 2 primary providers (at least 1 MD and 1 or more NPs and/or PAs per clinic). Thus, 2 providers per site will be recruited. Each will have 12 of their patients recruited (24 per clinic). Given our ~90% participation rate in previous FQHC studies^{25,108,109} and 93% SMASH participation rate, we anticipate no recruitment problems. The Medical University of South Carolina Family Medicine and Internal Medicine clinic population will be an additional recruitment resource if needed.

D.2. Participants: With consideration of the relevant biological variable of gender, we will recruit 192 AA 21-59 yr old uncontrolled HTNs with equal numbers of males and females that meet the following inclusion/ exclusion criteria: 1) SBP ≥ 140 mmHg on most recent clinic visit over last 12 mos and at BP screening and recruitment visits; 2) MPR < 0.85 over last 3 mos; 3) 24-hour SBP ≥ 130 mmHg (HTN cutoff) to help rule out white coat HTN.^{76,110} SBP used as selection variable since most AA HTNs < 60 have systolic or combination systolic/ diastolic HTN and for most patients, controlling SBP also results in DBP control;^{27,111,112} 4) no other known chronic diseases (e.g., diabetes, chronic kidney disease (GFR < 50 ml/1.73 m²/min), cancer, renal dialysis, heart attack, coronary artery bypass, arterial stent, substance abuse (e.g., > 21 drinks/week), psychiatric illness, Beck Depression Inventory¹¹³⁻¹¹⁵ > 13 , able to speak, hear and understand English; take own BP and meds; 6) owns smart phone with current data plan; 7) primary care MD's assent patient able to participate and 8) no planned pregnancy or vulnerable population (e.g., pregnant or nursing women, prisoners).

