Cochran-Mantel-Haentzel chi-square tests of differences in % of patients being >0.90 med adherent and % of patients within JNC8 guidelines for BP control (<140/90 mmHg) at the 6 month visit (primary endpoint) between the two groups (SMASH; enhanced SC). Type I error rate was 0.05 (two-sided). Sample size was adjusted to account for the cluster randomization scheme, using variance inflation factor (VIF) method.¹⁴⁸ Power and sample size estimates were performed for within-clinic sample sizes of 22 subjects for 4 clinics per group, assuming ICCs ranging from 0.0 to 0.05. The ICC from our feasibility trials for primary outcomes of electronic med tray based MA and SBP was estimated at 0.04. For an ICC of 0.04 the proposed sample size of 22 per clinic and 4 clinics per group provides at least 90% power to detect a difference in the assumed 6-month MA/BP control rates between the 2 groups (difference of $\geq 30\%$ between SMASH and SC based on feasibility trials' results).^{22,23,25,26} For the proposed study, for calculation of the VIF we used the conservative absolute ICC value of .04 for a final sample size 176. We inflated that by 10% (N=192) to account for greater than expected attrition across the trial. Conservative estimates for expected MA (or BP control) proportions were used for power calculations; proportions observed in our SMASH feasibility studies were 89% vs. 0%, N=19 for MA based upon MedMinder^{22,23} and for resting SBP, an average of 90% vs. 10% for the three trials lasting 3 and 6 months and the recent 12-month follow-up (n=19,²² n= 22,²⁵ n= 24,²³ n=19,²²). For secondary continuous outcomes of 24-hr BP (and MPR derived MA scores) for longitudinal analyses [assuming 4 intervention time points (months 3, 6, 12, and 18), level of significance = 0.05 (two-tailed), correlation among repeated measures (ICC ≤ 0.5)], we will have 90% power to detect a 0.48 standardized effect size (i.e., Cohen's d effect size). A standardized effect size of 0.48 sd is equivalent to a raw effect size ranging from 2.4 to 4.3 mmHg (raw scale units) for difference in SBP change from baseline between the groups for a range of sd from 5.0 to 9.0 mmHg, based upon our SMASH feasibility data.^{22,23,25,26} For resting DBP based upon our SMASH findings, this equates to a difference of 1.3 to 3.3 mmHg assuming sd ranging from 2.0-5.0 mmHg. SMASH findings for the tray derived monthly MA scores revealed a difference in MA score changes between the groups from baseline to 3 month of 28% (sd=6.2).^{22,23} Assuming similar adherence in both groups through the 6-month trial, we will have at least 94% power to detect differences in adherence change scores as small as 10% (with sd up to 15).

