
For AIMS 2: secondary outcomes (changes in SDT constructs [i.e., competence & autonomous motivation], % reaching & sustaining 24-hr BP control [<130/80 mmHg], therapeutic inertia (i.e., % making med change in patient's EHR & script delivery to patient or pharmacy within 24 hours of subject's clinic visit and/or receiving BP info report)⁷² and **AIM 3: exploratory outcomes** (cost effectiveness; changes in TC, LDL, HgA1c, blood glucose) in the intent-to-treat sample, we have 80% power to detect a difference of 0.53 sd between the 2 groups assuming $\alpha = 0.05$ (Type I error rate), two sided; independent sample t-test comparison of means; equality of variance between groups. For 24-hour BP, we will have > 85% power to detect a 30% difference in % reaching 24-hr BP control between groups. Our 24-hr BP data from a subgroup (N=12) of FQHC AAs in the feasibility trial found 85% of the SMASH group vs 25% of the SC group achieved 24-hr BP control at 6 mos.

D.9. Data Management & Quality Control: Quality control checks of anthropometrics/BP evaluations & 24-hr BP protocol delivery will be run on random selection of 10% of subjects per mo & protocol retraining conducted as needed. Questionnaire data will be directly captured via REDCap (HIPAA compliant, web-based app) & overseen by [name] and [name]. Clinic data (e.g., anthropometrics, BP) & EMR derived data (e.g. TC, HgA1C) will be double entered with discrepancies resolved by [name]. Data will be reviewed on twice-monthly basis. Outlying, inconsistent data values, as well as missing data, will be targets of the data quality review. Issues will be communicated to Drs. [name], [name] and [name] for resolution.

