D.10. Quantitative Analyses: AIM1 Primary outcome measures are % of subjects with >0.90 MA from MedMinder and % within JNC8 clinic resting BP guidelines (<140/90 mmHg). Secondary analyses will assess resting & ambulatory BP levels (e.g., 24-hr, daytime/nighttime BP level changes) & MA indices (i.e., MPR score changes). Intent-to-Treat (ITT) sample analyses will be used along with multiple imputation methods for missing end-of-study outcomes.^{149,150} To assess relationships between intervention outcomes and intervention status (SMASH or SC) at end of the active trial period (6-mo visit, primary endpoint), two-sided Cochran-Mantel-Haentzel chi-square tests for unadjusted differences in proportions will be used. Adjusted differences in proportions at the 6-mo visit will be compared using logistic regression. To assess relationships over time, we will use a generalized linear mixed models (GLMM; generalized estimation equation [GEE]-type models) analytic model with group (SMASH vs SC) & time (3, 6, 12 & 18 months) included as fixed effects and FQHC practice site as a random effect to account for clustering within FQHC practice site/MD.¹⁵¹⁻¹⁵³ In the first set of models, baseline measurement of the dependent variables (e.g., MA or BP levels) will be included as adjustment variable. The test of primary interest is F-test for the treatment x time interaction, which will reflect a difference in change between the 2 groups over the study. If a statistically significant treatment x time

interaction is found, we will obtain odds ratios for SMASH vs SC groups at each of the study time points.

A mixed effects model (MEM) will be used to compare the primary continuous outcome measures (e.g., tray or MPR derived MA scores or BP levels) for the two groups over the study period. Modeling will be carried out as described above. We will estimate resting and 24-hr BP changes and MA (MPR) changes for each subject over the trial (baseline, 3, 6, 12 & 18 months) and the within subject longitudinal trajectories (e.g., slopes) and summarize as the mean longitudinal trajectory within each group. ICCs and variance estimates will be obtained of efficacy outcomes and covariance structure of the longitudinal scores for determination of sample size (and hence adequate power) for a future effectiveness RCT.

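### D.8's 90% power for a 30-point difference makes no allowance for having only 8 randomised clinics: on 6 df it is about 80–85% where the plan's own formula supports 90%, and about 73–75% at the FQHC pilot's BP control rates

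*Combined protocol and SAP*

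**What the plan says.** D.1 sets the design: "We will use the 8 practice sites in a 2 arm RCT design (n=192) with clinic as unit of randomization", and the patient as the unit of analysis. D.8 bases power for the two primary proportions (adherence above 0.90, resting BP below 140/90 mmHg) on a two-sided chi-square test at 6 months with a 5% type I error. On clustering it says: "Sample size was adjusted to account for the cluster randomization scheme, using variance inflation factor (VIF) method". Power was computed for "within-clinic sample sizes of 22 subjects for 4 clinics per group, assuming ICCs ranging from 0.0 to 0.05"; an ICC of 0.04 was carried into the final calculation, giving 176 patients, raised to 192 for attrition. The result is stated as follows: the sample "provides at least 90% power to detect a difference in the assumed 6-month MA/BP control rates between the 2 groups", the difference being at least 30 points. The arm rates behind this are called conservative but are not given.

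For the secondary outcome of 24-hour BP control, the Aim 2 part of D.8 says "we will have > 85% power to detect a 30% difference in % reaching 24-hr BP control between groups".

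D.10 then specifies, for the 6-month endpoint, that "two-sided Cochran-Mantel-Haentzel chi-square tests for unadjusted differences in proportions will be used". Practice site enters as a random effect only in the longitudinal model, and no denominator degrees of freedom are given there. Neither D.8 nor D.10 mentions a correction for a small number of clusters.

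**The concern.** The variance inflation factor corrects the size of the variance. It does not allow for that variance having to be estimated from very few clinics. With 4 clinics per arm, a comparison that respects the randomisation has 2 × (4 − 1) = 6 degrees of freedom, and its two-sided 5% critical value is 2.447 rather than 1.960. Power read from the normal distribution is therefore too high for a test that holds its 5% level.

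What is at stake is the reading of a null result. If the true benefit were 30 points, readers of D.8 would put the chance of missing it at 10% or less, when it could be 15–20% or more. D.10 also intends to use this trial's ICCs and variances to size a later effectiveness trial, so the same method could carry over.

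**Working it through.** **Inputs from the documents.** Two-sided α = 0.05, 22 per clinic, 4 clinics per arm, ICC 0.04 and a 30-point difference (all D.8); clinic as the unit of randomisation (D.1). SC rates mentioned: 0% for adherence and an average of 10% for resting SBP (D.8); 25–40% for BP control in the FQHC feasibility trial (C.1.4, trial 2); 25% for 24-hour control (D.8). **Assumed:** the arm rates used for power, shown as a range.

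**Step 1: cluster inflation.** VIF = 1 + (22 − 1) × 0.04 = 1.84. Effective size per arm = 88 / 1.84 = 47.8.

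**Step 2: reproduce the plan's figures.** Normal power with pooled variance under the null is Φ[(0.30 − 1.96 × SE₀) / SE₁], where SE₀ = √[2p̄(1 − p̄)/47.8] and SE₁ = √[(p₀q₀ + p₁q₁)/47.8].

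- 10% v 40%: SE₀ = 0.0885, SE₁ = 0.0831, so Φ(1.52) = 93.6%. This agrees with the 90% claim.
- 25% v 55%: SE₀ = 0.1002, SE₁ = 0.0954, so Φ(1.09) = 86.1%. This agrees with the 85% claim for 24-hour control. Without the inflation factor the figure would be about 98%.
- Working back from 90% power, the required total is 174 at 15% v 45% and 178 at 16% v 46%, on either side of the plan's 176. The mirror-image pair, 55% v 85%, also gives 174.

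**Step 3: the same variance on 6 df.** Noncentrality = 0.30 / SE₁; power = P(T′(6, noncentrality) > 2.447). For 10% v 40%: 0.30 / 0.0831 = 3.61, power 85.1%.

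| SC v SMASH | Normal, pooled | Normal, unpooled | 6 df |
|---|---|---|---|
| 0% v 30% | 99.1% | 99.5% | 96.2% |
| 5% v 35% | 96.7% | 97.7% | 90.6% |
| 10% v 40% | 93.6% | 95.1% | 85.1% |
| 16% v 46% | 90.0% | 91.8% | 79.7% |
| 20% v 50% | 88.0% | 90.0% | 77.0% |
| 25% v 55% | 86.1% | 88.2% | 74.6% |
| 30% v 60% | 85.0% | 87.1% | 73.2% |
| 35% v 65% | 84.6% | 86.8% | 72.8% |

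Power is symmetric: 60% v 90% equals 10% v 40%, and 40% v 70% equals 30% v 60%.

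**Step 4: separate the two causes.** At 25% v 55% the pooled normal formula is already 90 − 86.1 = 3.9 points below 90%; moving to 6 df takes off a further 86.1 − 74.6 = 11.5 points. At 35% v 65% the two parts are 5.4 and 11.8 points.

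**Step 5: checks.** A beta-binomial simulation of a t-test on clinic proportions (200,000 trials) gave 84.3% (10% v 40%), 73.3% (25% v 55%) and 71.6% (35% v 65%), within about 1 to 1.5 points of the formula. With all 24 per clinic retained, 6-df power is 86.5%, 78.8%, 76.4% and 75.0% at SC rates of 10%, 20%, 25% and 30%. At the upper ICC in D.8, 0.05, with 22 per clinic, it is 81.2% (10% v 40%) and 68.7% (30% v 60%). For 90% power on 6 df at ICC 0.04 the difference must be 32.8, 36.1, 36.9 or 37.2 points at SC rates of 10%, 20%, 25% and 30%.

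**The case against.** The strongest reply is that D.8 names its test, its cluster adjustment and its ICC, and its figures follow from them. That stands: both figures reproduce, so this is a limitation of the method and not an arithmetic slip. It does not rescue the claim, however. A chi-square that ignores clinic has a true type I error of about 2 × [1 − Φ(1.96/√1.84)] = 15% at ICC 0.04, and power quoted at 5% must belong to a test that holds 5%. Nor can clinic serve as a stratum in the Cochran-Mantel-Haenszel test, because each clinic sits wholly in one arm.

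A second reply is that the pilot differences were far larger. This is true and it limits the consequence: at 10% v 90% and 25% v 85%, the pilot rates in D.8, 6-df power exceeds 99%, and at a 40-point difference (25% v 65%) it is 94%. The shortfall concerns the 30-point floor that D.8 chose to quote.

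Third, a reader might infer that neither primary outcome has the stated power. The documents do not support that. The only SC adherence rate in D.8 is 0%, and at 0–5% the pooled 6-df test has 91–96% power. The result there depends on the test: a Welch t-test simulates at 83–87%.

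Fourth, the Aim 2 text does not say that the 24-hour figure used the inflation factor, and the sentence before it describes an ordinary t-test. The link is an inference from the match at 25% v 55%.

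Finally, baseline adjustment might recover some power, but it is not part of D.8's calculation.

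**Conclusion.** The point holds in a limited form. For a 30-point difference at ICC 0.04 with 22 per clinic, the stated 90% becomes about 85% (10% v 40%) to 80% (16% v 46%) on 6 df, over the range where the plan's formula supports 90% with an SC rate of 10% or above. The chance of missing a true 30-point benefit there is 15–20%, not at most 10%. At the FQHC pilot's 25–40% SC control rates power is about 73–75%. It would be wrong to put that whole gap down to the degrees of freedom, because roughly 4 to 5 points come from rates at which the plan's own formula already falls short. For adherence the claim stands only if the SC rate is about 5% or less. The 24-hour BP control figure becomes about 75%, on the inference that it used the same method.

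A reader might also infer that the trial is underpowered for the effect its investigators expect. The documents do not show that, since power remains above 99% at the pilot differences. All figures rest on assumed arm rates and on the plan's ICC.

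**What to change.** In D.8, state the assumed arm rates for each outcome and replace both claims with noncentral-t power on 6 df. For example: with 22 patients per clinic, 4 clinics per arm and ICC 0.04, power for a 30-point difference is about 85% at 10% v 40%, 77% at 20% v 50%, 75% at 25% v 55% and 73% at 30% v 60%; 90% power needs a difference of about 33 to 37 points at SC rates of 10–30%. Restate 24-hour BP control as about 75% at 25% v 55%, and say whether the inflation factor was used.

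In D.10, state that the 6-month comparison uses a test that accounts for clinic with 6 df: a t-test on clinic proportions, or a model with site as a random effect and small-sample degrees of freedom. Without this, the restated power would describe a test that the plan does not run.

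The cost is wording in two sections, a less favourable stated power, and a stricter critical value for the 6-month test. No change in enrolment is asked for.

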
NARRATIVE

Interventions that address medication nonadherence among chronic disease patients must be acceptable, sustainable, and easily disseminated by clinicians. We will test and further refine a smartphone delivered, tailored medical regimen self-management program for African Americans with uncontrolled hypertension that will facilitate medication adherence, BP control, and clinician oversight. With demonstrated effectiveness in future trials, the intervention will ameliorate the risk of future comorbidities (e.g., hypercholesterolemia, diabetes), cardiovascular events (e.g., kidney failure, stroke, heart attack) and associated premature mortality.

INTRODUCTION TO REVISED APPLICATION

The thorough reviews guided our new pilot research on Smart Phone Medication Adherence (MA) Stops Hypertension (SMASH) developed for African Americans (AAs). We ran a 3rd feasibility trial (n=24), published 3 articles (2nd mHealth attitudes survey and results of 2 feasibility trials), made SMASH refinements based upon subjects' post trial feedback and made changes in our approach and analyses. **Strengths:** high clinical significance, no RCTs using mHealth in this domain, focus on both MA and BP control, use of 24-hr BP, rigor of using RCT design, time and attention control group and follow-up assessments, intervention theoretically driven, use of cultural tailoring and strategies for low literacy, promising preliminary data, cost effectiveness analyses, excellent environment and investigators. **Weaknesses:** Outlined below with Reviewer (R) comments in *italics* followed by our responses. Text changes are noted by a vertical line in the right margin.

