Eligible participants were randomly assigned to either standard care (SC) or SMASH. The SMASHers had the reminder functions of their med tray **enabled** and received a Bluetooth enabled BP monitor (see section D.5a). A smart phone received and sent encrypted BP data and delivered automated SMS reminders to measure BP. SMASHers received reinforcement/motivational phone calls from the project manager. These calls aimed to improve MA by increasing the SDT construct of competence for MA and identifying subject's beliefs, values, and short-term life goals and linking them to desirable behavior change. Providers received weekly summary reports of patient MA and BP readings. The SC cohort continued to use the MedMinder with reminder functions **disabled**. Participation rate (% approached who agreed to engage in 1-month med intake screening) was 75% and recruitment rate (% who were eligible following screening who enrolled in trial) was 91%. The SMASH group reported a high degree of overall satisfaction with the mHealth system (4.8/5 Likert Scale) and perceived SMASH to be easy to learn (4.7/5) and use (4.8/5.) HTN med adjustments occurred more often and within ~24 hours of clinic visit (or weekly report) in the SMASH cohort vs the SC cohort. All occurred in the trial's first month. The prototype SMASH system appeared safe and highly acceptable to patients and providers. As shown in Figs. 2a and 2b the SMASH cohort exhibited clinically relevant improvements in time-stamped MA and SBP compared to the SC cohort.^{22,23} At 3 months, 90% of SMASHers met JNC8 BP guidelines compared to 25% in the SC cohort.

Since the initial grant submission we published a 12 month follow-up using clinic BP readings 6 and 12 months post-trial completion.²⁴ Clinic nurses took the BPs. They were unaware of patients' previous involvement in the study nor did they use a standard BP protocol as used in our trial. Nevertheless, as shown in Fig.3, the SMASH group maintained significantly lower SBPs compared to the SC group. At months 6 and 12, 63-88% were below the JNC8 BP control cutoffs compared to 25-38% for the SC group.

[figure not shown]

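### D.8 prints a pilot control rate and a DBP conversion that the plan's own figures contradict, and its 90% power for BP control holds only for some standard-care rates

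*Combined protocol and SAP*

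**What the plan says.** Section D.8 (Sample Size Justification & Power Calculations) rests the primary power on a two-sided 5% test, 22 patients in each of four clinics per arm, and a difference of at least 30 percentage points at 6 months. It states: "For an ICC of 0.04 the proposed sample size of 22 per clinic and 4 clinics per group provides at least 90% power". On the inputs it says: "we used the conservative absolute ICC value of .04 for a final sample size 176", later inflated to 192 for attrition. On the rates it says only: "Conservative estimates for expected MA (or BP control) proportions were used for power calculations". It then lists what the pilots observed, including "for resting SBP, an average of 90% vs. 10% for the three trials lasting 3 and 6 months and the recent 12-month follow-up".

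Section C.1.4 reports the pilots one by one:
- Trial 1: "90% of SMASHers met JNC8 BP guidelines compared to 25% in the SC cohort".
- Trial 1 follow-up: "At months 6 and 12, 63-88% were below the JNC8 BP control cutoffs compared to 25-38% for the SC group".
- Trial 2, in the health-centre network that will supply this trial: SMASH 90-100%, SC 25-40%.
- Trial 3: SMASH 57-86%, SC below 25%.

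For continuous outcomes, D.8 converts 0.48 SD to 2.4-4.3 mmHg of SBP for SDs of 5.0-9.0. It then says that this corresponds to 1.3-3.3 mmHg of resting DBP for SDs of 2.0-5.0.

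**The concern.** Two printed figures can be checked against the plan itself, and both fail. The third matter is the primary power. For a fixed 30-point difference, power depends on where the two rates lie, and D.8 does not say. The only SC figure for BP control in that paragraph is the 10% that C.1.4 contradicts, and at 10% the power claim would be comfortable.

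The stake is how a null BP-control result would be read. A reader would assume at most a 10% chance of missing a true 30-point difference. If SC control is as in the same-network pilot, that chance is about 12-15% at 176 patients, depending on the variance form.

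**Working it through.** **1. Pilot SC average.** Inputs are the C.1.4 SC rates and the sample sizes in D.8 (19, 22, 24, 19; total 84). The introduction to the revised application gives 24 as the size of the third trial: "We ran a 3rd feasibility trial (n=24").
- Lowest possible, trial 3 at 0%: (19×25 + 22×25 + 24×0 + 19×25)/84 = 1500/84 = 17.9%. Unweighted: 75/4 = 18.75%.
- Highest possible: (19×25 + 22×40 + 24×25 + 19×38)/84 = 2677/84 = 31.9%. Unweighted: 128/4 = 32.0%.
- Trial 3 rate needed for an average of 10%, others at their minimum: (10×84 − 1500)/24 = −27.5%, which is impossible.
- Without the follow-up, the floor is still 15.8% (16.7% unweighted). Without trial 3, it is 25%.
- The SMASH side spans 74.5-91.0% weighted, so 90% is possible but near the top.

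D.8 speaks of SBP and C.1.4 of control to the JNC8 limits. SBP control alone cannot be rarer than joint SBP and DBP control, so that difference cannot explain a lower figure.

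**2. DBP conversion.** The SBP line reproduces: 0.48×5.0 = 2.4 and 0.48×9.0 = 4.3. The DBP line does not: 0.48×2.0 = 0.96 and 0.48×5.0 = 2.4. The printed values are 1.3/2.0 = 0.65 SD and 3.3/5.0 = 0.66 SD.

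**3. Power for BP control at exactly 30 points.** Inputs are two-sided 5%, ICC 0.04 and four clinics per arm, all from D.8.
- 22 per clinic: VIF = 1 + 21×0.04 = 1.84; effective n per arm = 88/1.84 = 47.8.
- 24 per clinic (all 192 evaluable): VIF = 1 + 23×0.04 = 1.92; effective n per arm = 96/1.92 = 50.0.
- Power = Φ[(0.30 − 1.96×s0)/s1]. Here s1² = [p(1−p) + q(1−q)]/n and q = p + 0.30. With pooled variance s0² = 2r(1−r)/n, where r = (p+q)/2. With unpooled variance s0 = s1.

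Worked example, SC 25%, n = 47.8: s0 = 0.1002 and s1 = 0.0954, so (0.30 − 0.1964)/0.0954 = 1.09 and power is 86.1%.

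| SC rate | N=176 pooled | N=176 unpooled | N=192 pooled | N=192 unpooled |
|---|---|---|---|---|
| 10% | 93.6% | 95.1% | 94.6% | 95.8% |
| 16% | 90.0% | 91.8% | 91.3% | 92.9% |
| 20% | 88.0% | 90.0% | 89.4% | 91.2% |
| 25% | 86.1% | 88.2% | 87.6% | 89.6% |
| 35% | 84.6% | 86.8% | 86.2% | 88.2% |
| 40% | 85.0% | 87.1% | 86.6% | 88.5% |
| Power falls below 90% above SC of | 16.0% | 19.9% | 18.6% | 23.4% |
| and returns to 90% at SC of | 54.0% | 50.1% | 51.4% | 46.6% |

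The plan's statement is therefore reproduced at low SC rates and not at 25-40%. D.8's own claim of more than 85% power for 30 points in 24-hour BP control, where the pilot SC rate was 25%, agrees with the 86.1% above.

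**4. Size of the shortfall.** At N=176 with pooled variance, 90% power needs 31.9, 32.3, 32.4 and 32.2 points at SC 25, 30, 35 and 40%. At the narrowest pair in the same-network pilot (90% vs 40%), power is above 99.9%. At the least favourable averages from step 1 (about 75% vs 32%), it is about 99.4%. For adherence, with the pilot SC rate of 0%, a 30-point difference has 99.1% power.

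**The case against.** Several defences have force.

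**The documents show a conflict, not which side is wrong.** D.8's reference labels for its sample sizes do not include the publications of trial 3 or of the follow-up, so matching the sources is partly inference. This stands: the passages need reconciling, and D.8 need not be the one in error. The same applies to DBP, where the mmHg range, the SDs or the link to 0.48 SD could be the slip.

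**The 10% is background.** D.8 says that conservative rates were used for power and lists the observed rates separately. A reader might infer that 10% was the power input and that N is too small as a result. The documents do not show this, and correcting the 10% changes neither N nor power.

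**The threshold depends on unstated choices.** D.8 names no variance form, so the SC limit is a range of about 16-23%, not one value. D.8 also says 30 points or more, and larger differences are well powered.

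**The 25-40% is only a guide.** It comes from a pilot of 22 patients that skipped the one-month tray screening required here, so a lower SC rate is possible. That is a reason to show power over a range, not to leave the rates out.

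**The DBP slip does little harm.** Table 3 lists resting SBP as the BP measure, and the printed DBP range is wider than 0.48 SD implies, so it does not overstate sensitivity.

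A reader might also infer that D.8's other figures are miscalculated: 94% power for the adherence change, 90% at 0.48 SD and 80% at 0.53 SD. At ICC 0.04, simple methods give 89.7%, 83.6% and 72.7% with N=176, and 91.0%, 85.2% and 74.7% with N=192. But D.8 gives no clinic ICC for them and no numeric N. ICC 0.03 with N=192 gives 94.1%, 89.4% and 80.0%, although those inputs are back-solved. The longitudinal figure also depends on how baseline is handled. No error is shown.

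**Conclusion.** The point holds in three limited parts.
- The pilot SC average of 10% in D.8 conflicts with C.1.4, whose rates average about 18-32%. This assumes that both sections describe the same trials and allows trial 3 any SC rate from 0 to 25%.
- The DBP line is internally inconsistent: 0.65-0.66 SD is presented as 0.48 SD.
- The claim of at least 90% power for BP control is true only for some unstated rates. At exactly 30 points, ICC 0.04 and SC control of 25-40%, power is about 85-86% pooled or 87-88% unpooled at N=176. If all 192 are evaluable, it is about 86-88% or 88-90%.

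This is a shortfall of a few points of power at the smallest difference named. It does not make the trial underpowered for differences like those in the same-network pilot, and it gives no reason to change N or the tests.

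**What to change.** Text changes in D.8 and, if needed, C.1.4:

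1. Reconcile the pilot SC average so that the two sections agree, and identify which trial each sample size belongs to.
2. Make the DBP line consistent. Print 0.96-2.4 mmHg if the SDs of 2.0-5.0 stand, print SDs of about 2.7-6.9 (1.3/0.48 and 3.3/0.48) if the mmHg range stands, or drop the link to 0.48 SD.
3. State the SC and SMASH rates assumed for BP control. Give power for 30 points over a range of SC rates, including about 85-88% at 25-40% for N=176, and name the variance form and N.

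Optionally, state the ICC and N behind the 94%, 0.48 SD and 0.53 SD figures so that they can be compared with the primary calculation.

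The cost is editing only: no more patients or visits, and no change to N or the tests. The one downside is that the stated power becomes slightly less favourable.

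### The 6-month primary tests carry no correction for randomising eight clinics: type I error is about 15% at the plan's own ICC, and a second test is also described as primary

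*Combined protocol and SAP*

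**What the plan says.** Section D.1 randomises eight clinics and analyses patients. Section D.8 bases the sample size on a Cochran-Mantel-Haenszel (CMH) comparison "at the 6 month visit (primary endpoint) between the two groups (SMASH; enhanced SC"). It says: "Sample size was adjusted to account for the cluster randomization scheme, using variance inflation factor (VIF) method". The calculation uses 22 patients per clinic and four clinics per arm, "assuming ICCs ranging from 0.0 to 0.05", and settles on an ICC of 0.04.

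For the analysis at that same time point, section D.10 (AIM 1) says that "two-sided Cochran-Mantel-Haentzel chi-square tests for unadjusted differences in proportions will be used" and that "Adjusted differences in proportions at the 6-mo visit will be compared using logistic regression". It then moves to a model for change over time, and there it includes "FQHC practice site as a random effect to account for clustering within FQHC practice site/MD". About that longitudinal model it says: "The test of primary interest is F-test for the treatment x time interaction". Odds ratios at individual visits are conditional on that test: if a significant treatment x time "interaction is found, we will obtain odds ratios for SMASH vs SC groups at each of the study time points".

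The Introduction to Revised Application also says that clinic will enter the analysis as a random effect, and refers the reader to D.10 for this.

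**The concern.** Patients from one clinic share providers and setting, so their outcomes are correlated. A patient-level chi-square or logistic regression that treats them as independent understates the variance of the difference between arms. The p-values for both primary outcomes (adherence above 0.90 and BP below 140/90 mmHg) would then be too small and the intervals too narrow, and a chance difference between clinics could be read as a SMASH effect. Enlarging the sample by a VIF protects power but does not repair the variance used in the test.

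The CMH label does not supply the correction. D.10 names no strata, and stratifying by clinic is impossible: each clinic lies wholly in one arm, so its stratum contributes nothing to the statistic.

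The second difficulty is which result decides the trial. The 6-month visit is the primary endpoint, but primary status is also given to an interaction test over months 3, 6, 12 and 18 with baseline as a covariate. A SMASH benefit that is constant from month 3 onward produces no interaction, and the month-6 odds ratio from that model would then not be obtained.

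**Working it through.** **Inputs.** From D.8: two-sided alpha 0.05; 4 clinics per arm; m = 22 analysed per clinic (88 per arm); ICC 0.04, range 0 to 0.05; difference of at least 30 points; power at least 90%. From D.1: 24 recruited per clinic. The two rates behind the 30 points are not stated, so control rates of 10%, 25% and 35% are assumed below.

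**1. The plan's power figure.** VIF = 1 + (22 − 1) × 0.04 = 1.84, so the effective sample is 88/1.84 = 47.8 per arm. Two-proportion power is then 94% for 10% v 40%, 86% for 25% v 55% and 85% for 35% v 65%. The stated minimum of 90% is met at a 10% control rate but not at 25% or 35%. Without the assumed rates it can be neither confirmed nor refuted.

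**2. Type I error of the uncorrected chi-square.** Clustering multiplies the true variance by the VIF while the test assumes 1, so actual size = 2 × [1 − Φ(1.96/√VIF)].

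| ICC | VIF, m = 22 | Size | VIF, m = 24 | Size |
|---|---|---|---|---|
| 0 | 1.00 | 5.0% | 1.00 | 5.0% |
| 0.01 | 1.21 | 7.5% | 1.23 | 7.7% |
| 0.02 | 1.42 | 10.0% | 1.46 | 10.5% |
| 0.03 | 1.63 | 12.5% | 1.69 | 13.2% |
| 0.04 | 1.84 | 14.8% | 1.92 | 15.7% |
| 0.05 | 2.05 | 17.1% | 2.15 | 18.1% |

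Beta-binomial simulation (200,000 trials per setting, 4 v 4 clinics, ICC 0.04, event rates 10% to 50%) gave 14.7–15.4% with 22 per clinic and 15.7–16.0% with 24.

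**3. Interval width.** Uncorrected width relative to correct width is 1/√VIF: 1/√1.84 = 0.74 and 1/√1.92 = 0.72, so intervals are 26–28% too narrow. With the 6 between-clinic degrees of freedom (critical value 2.447), the ratios become 0.74 × 1.96/2.447 = 0.59 and 0.72 × 1.96/2.447 = 0.58, or 41–42% too narrow.

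**4. Logistic regression without a clinic term.** This was simulated (6,000 trials, event rates 25% and 50%) with one assumed prognostic patient covariate, log odds ratio 0.5 or 1.0 per SD. Type I error was 14.6–18.6% at ICC 0.04 and about 5% at ICC 0. Covariate adjustment does not remove the problem.

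**5. Type I error of the alternatives at ICC 0.04.**
- Clinic-level t-test on 6 df: 4.9–5.2%.
- CMH chi-square divided by a VIF fixed at ICC 0.04: 4.3–5.4%.
- Random-intercept logistic model (3,000 trials): 9.2–11.6% with a normal reference, 3.7–4.5% with 6 df.

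**6. Power of the alternatives, 22 per clinic, ICC 0.04.**

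| Test | 10% v 40% | 25% v 55% | 35% v 65% |
|---|---|---|---|
| VIF-adjusted chi-square | 94% | 86% | 85% |
| Mixed logistic model, 6 df | 89% | 78% | 76% |
| Clinic t-test, 6 df | 84% | 73% | 71% |

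The noncentral t formula gives 85%, 75% and 73% for the last row. For the 90% v 10% reported from the feasibility trials, power exceeds 99% for the t-test and the VIF-adjusted chi-square.

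**The case against.** **The plan does not ignore clustering.** The Introduction promises clinic as a random effect, and the omission can be read as an intention not carried into two sentences of D.10. That is fair as to intent. But the Introduction defers to D.10, which attaches the random effect only to the longitudinal model, and a chi-square test has no random effect. An analyst following D.10 would run the 6-month tests uncorrected.

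**The ICC of 0.04 may not apply to the binary endpoints.** D.8 gives it for tray-based adherence and SBP without saying whether these are the continuous or the dichotomised measures, and the feasibility trials had only 19 to 24 patients. If it is a continuous-scale ICC, dichotomising a normal variable gives binary ICCs of about 0.014, 0.022 and 0.026 at event rates of 10%, 25% and 50%. Type I error is then 8.5–11.4% with 22 per clinic. This stands as a qualification of the size, but the test remains clearly anti-conservative.

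**The F-test may be primary only within the longitudinal models.** That is a natural reading, since the sentence sits under the analysis over time and both D.8 and D.10 make month 6 the primary endpoint. D.10 does not say so, however, and on that reading the uncorrected 6-month test alone decides the trial. It is also true that a constant benefit would show in that model's group main effect, but the plan designates the interaction instead. This part needs only a clarification of wording.

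**Conclusion.** The concern holds. As written, the 6-month tests of both primary outcomes have a type I error of about 15% at the plan's ICC (14.8% with 22 per clinic, 15.7% with 24), roughly three times nominal. The size rests on ICC 0.04 applying to the binary endpoints and on the tests being run exactly as D.10 states. It ranges from 5% to 17–18% over the plan's own ICC range. The covariate-adjusted logistic and mixed-model figures depend on smaller simulations, and the former also on assumed covariate effects, so they are indicative. The double use of primary status is the lesser fault, but it leaves unclear which result decides the trial. The missing correction must be fixed before analysis.

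**What to change.** In D.10, name one primary 6-month analysis with clinic as the randomised unit, and state that the treatment-by-time F-test is secondary. Any of these would serve:

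- **Clinic-level t-test** on the eight clinic proportions with 6 df, using covariate-adjusted clinic residuals for the adjusted comparison.
- **Logistic mixed model** with a clinic random intercept and small-sample df. The df must be specified, because a normal reference leaves type I error at 9–12%.
- **Minimum change:** keep the CMH test and divide its chi-square by the VIF, with the ICC fixed in advance. With the VIF fixed at ICC 0.04, type I error is about 6.3–6.4% if the true ICC is 0.05, about 10.5% if it is 0.08, and 0.8% if it is 0. Estimating the ICC from the trial's eight clinics instead gave 7.6–7.8% at a true ICC of 0.04.

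D.10 uses multiple imputation for missing end-of-study outcomes, so also state that the imputation model respects clinic and how results are pooled with few df. In D.8, give the two assumed rates and say whether the ICC is on the binary scale, then restate power for the chosen test.

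The cost is SAP wording and a revised power statement, with no new data. Intervals will be wider, and power for a 30-point difference may fall below the stated 90%, as tabulated above.
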